11.6 Sample size calculation

The sample size text below still applies following amendment 6, as the potential increase in number of patients treated is not so much to increase power of the study but to provide a treatment option for C5 variant PNH patients without an alternative. Notwithstanding that, if further patients are recruited then overall power will increase and the calculations below may then also be applicable to C5-variant patients only. If no further patients are recruited, the below text remains valid.

Commercially Confidential Information

11.7 Power for analysis of key secondary variables

Not applicable.

11.8 Interim analyses

Commercially Confidential Information

12 Ethical considerations

12.1 Regulatory and ethical compliance

This clinical study was designed and shall be implemented and reported in accordance with the ICH Harmonized Tripartite Guidelines for Good Clinical Practice, with applicable local regulations (including European Directive 2001/20/EC, US Code of Federal Regulations Title 21, and Japanese Ministry of Health, Labor, and Welfare), and with the ethical principles laid down in the Declaration of Helsinki.

12.2 Responsibilities of the investigator and IRB/IEC

Before initiating a trial, the investigator/institution should obtain approval/favorable opinion from the Institutional Review Board/Independent Ethics Committee (IRB/IEC) for the trial protocol, written informed consent form, consent form updates, subject recruitment procedures (e.g. advertisements) and any other written information to be provided to subjects. Prior to study start, the investigator is required to sign a protocol signature page confirming his/her agreement to conduct the study in accordance with these documents and all of the instructions and procedures found in this protocol and to give access to all relevant data and records to Novartis monitors, auditors, Novartis Quality Assurance representatives, designated agents of Novartis, IRBs/IECs, and regulatory authorities as required. If an inspection of the clinical site is requested by a regulatory authority, the investigator must inform Novartis immediately that this request has been made.

For multi-center trials, a Coordinating Investigator will be selected by Novartis around the time of Last Patient Last Visit to be a reviewer and signatory for the clinical study report.

12.3 Publication of study protocol and results

Novartis assures that the key design elements of this protocol will be posted in a publicly accessible database such as clinicaltrials.gov. In addition, upon study completion and finalization of the study report the results of this trial will be either submitted for publication (e.g. peer-reviewed journal) and/or posted in a publicly accessible database of clinical trial results.

13 Protocol adherence

This protocol defines the study objectives, the study procedures and the data to be collected on study patients. Additional assessments required to ensure safety of subjects should be administered as deemed necessary on a case by case basis. Under no circumstances should an investigator collect additional data or conduct any additional procedures for any research related purpose involving any investigational drugs.

Investigators must apply due diligence to avoid protocol deviations. If the investigator feels a protocol deviation would improve the conduct of the study this must be considered a protocol amendment, and unless such an amendment is agreed upon by Novartis and approved by the IRB/IEC/REB it cannot be implemented. All significant protocol deviations will be recorded and reported in the CSR.

1.1 Scope

The RAP documents contain detailed information to aid the production of Statistics & Programming input into the Clinical Study Report (CSR) for trial “**CLFG316X2201**”.

Module 3 (M3) provides the description of the statistical methodology used to analyze the data, **Module 7 (M7)** details the presentation of the data, including shells of summary tables, figures and listings, and **Module 8 (M8)** contains programming specifications e.g. for derived variables and derived datasets, to support the creation of CSR outputs.

1.2 Changes to RAP documentation (M3)

Refer to corresponding guidances and NIBR RAP Addendum template for detailed information on the requirements of documenting changes to RAP documentation.

For the statistical methodology (M3), any major changes to the statistical methodology should be reflected in the RAP M3 documentation via version control (M3 amendment) (new document version to be approved by the trial team as the original module).

Such major changes could include (but are not limited to):

- change in statistical methodology
- substantial change in (derivation of) main endpoint
- substantial change in study design (e.g. protocol amendment introducing new multiple-dose cohorts in a so far single-dose trial)

Such changes may also require a protocol amendment to ensure consistency. In addition they need to be mentioned (high-level) in the CSR (section for changes to planned analysis).

Minor changes to the RAP M3 documentation can be captured e.g. by a study note to file / note in RAP Addendum or within the CSR itself. Minor changes include, but are not limited to, changes related to exploratory endpoints, addition of further exploratory analyses, changes to the extended scope of interim analyses. Corrections of typographical errors or modification of spelling (from English to American, for example) do not need to be incorporated into the RAP M3 documentation.

Analyses and outputs related to additional exploratory ad-hoc requests used for reporting are regarded minor changes and should be documented in the RAP addendum (no RAP amendment necessary).

2 Study objectives and design

2.1 Study objectives

2.1.1 Primary objective

- To assess the effect of LFG316 on the reduction of intravascular hemolysis in PNH patients

2.1.2 Secondary objective

- To assess the tolerability and pharmacokinetics of LFG316 in patients with PNH

2.1.3 Exploratory objectives

Commercially Confidential Information

2.2 Study design and treatment

This is an open-label, non-controlled study in patients with PNH. Approximately 10 patients will be enrolled in the study. Commercially Confidential Information

The study drug will be administered via i.v. infusion at the dose level of 20 mg/kg every 14 days. Patients participating in study will have an option to either complete period 3 Follow up and Study Completion evaluation or continue in study period 4 that is pre-requisite to join the long-term extension study CLNP023C12001B, that is separate to this study protocol. Patients who are potentially eligible and willing to participate in the LNP023 long-term extension study will join period 4, where treatment will be converted from LFG316 to LNP023 200 mg b.i.d.

The study will consist of a 60-day screening period to assess eligibility and conduct vaccinations if required (for all patients not previously vaccinated at least 2 weeks prior to first dosing or if prior vaccination cannot be confirmed). An extensive screening window (up to 60 days) is planned in order to comply with local vaccination requirements, if available and deemed necessary at the investigator's discretion. Safety evaluation assessments requiring blood and urine samplings, pregnancy test, pulmonary function test, ECG, patient reported outcomes, and assessment of number of blood transfusions should be performed no longer than 4 weeks prior to the planned dosing day. Subjects who meet the eligibility criteria at screening will be admitted to baseline (Day 1) evaluations. The patients will enter treatment period 1, and will receive infusions of LFG316 every 14 days, days 1, 15 and 29 (3 administrations).

At the end of period 1, efficacy on hemolytic activity by serum LDH will be assessed. All patients will then be allowed to enter the optional treatment period 2, and will receive infusions of LFG316 every 14 days, and undergo the efficacy, PK, CCI and safety assessments for additional 48 weeks.

Following the 48-week treatment period 2, LFG316-responsive patients (assessed based on investigator's judgment) will be allowed to enter an additional third extension period of up to 260 weeks (extension period 3).

The LFG316 treatment for all patients will be completed by end of 2021 regardless of each individual treatment period.

[figure not shown]
Patients participating in extension period 3 will roll over from the last dosing visit of period 2 to the first visit (which includes drug administration) of period 3. The same dosing interval applied in Period 1 and 2 will be applied between the last dosing visit of Period 2 and the first visit of Period 3.

Period 4 can be initiated as directed by Sponsor and will last approximately 21 weeks. During the first 4 weeks patients will continue to receive LFG316 20 mg/kg every two weeks (total of two administrations) in addition to oral administration of LNP023 200 mg b.i.d. After 4 weeks, patients will discontinue LFG316 and will proceed with LNP023 200 mg b.i.d. monotherapy for approximately 16 weeks (+/- 28 days). Patients who participate in period 4 can join the long-term extension study CLNP023C12001B as soon as their eligibility is confirmed and study CLNP023C12001B is open to receive patients. There should be no LNP023 treatment gap between the studies. Please refer to [Section 7.1](#) of the protocol for guidance regarding safety monitoring and LNP023 down-titration in case of LNP023 treatment discontinuation.

For patients not participating in the period 4, the extension period 3 will be followed by a Study Completion evaluation approximately 8 weeks after the last drug administration. Patients who discontinue treatment prematurely during any of the study periods will be followed for 8 weeks after discontinuation, and will similarly undergo a study completion visit. The 8 weeks follow-up period will start the day after the last drug administration (both for patients completing treatment and patients prematurely discontinuing), and will comprise one visit after approximately 4 weeks, and a study completion visit after approximately 8 weeks from the last drug administration. Safety assessments will include physical examinations, ECGs, vital signs, standard clinical laboratory evaluations (hematology, blood chemistry, urinalysis) and adverse event monitoring.

Patients participating in period 4, will complete their Study Completion evaluation approximately one week after last LNP023 treatment administered as a part of this study.

Figure 2-1 Study design

*Period 4 is applicable only for the patients who are potentially eligible and wish to participate in the long-term extension study CLNP023C12001B

**+/-28 days

3 First interpretable results (FIR)

Commercially Confidential Information

Commercially Confidential Information

4 Interim analyses

Commercially Confidential Information

5 Statistical methods: Analysis sets

For subjects for which the actual treatment received does not match the planned treatment the treatment actually received will be used for the analysis. The study has four parts, the safety and efficacy analysis will be presented for period 1, period 2 and period 3 combined, and separately for period 4 unless otherwise stated below/in the output shell.

All subjects that received study drug will be included in the safety analysis set.

The PK analysis set will include all subjects with available PK data and no protocol deviations with relevant impact on PK data.

Commercially Confidential Information

6 Statistical methods for Pharmacokinetic (PK) parameters

6.1.1 Variables

The following pharmacokinetic parameters will be determined (if feasible) using non-compartmental method(s) with Phoenix WinNonlin (Version 6.2 or higher): AUC(0-tlast), AUC(0-t), Cmax, tmax, Cmax/D, AUC/D. The linear trapezoidal rule will be used for AUC calculation. For LNP023 only pre-dose and 2 hour concentrations will be determined in period 4.

6.1.2 Descriptive analyses

Total LFG316 concentration data will be listed by patient, and visit/sampling time point while pharmacokinetic parameters will be listed by patient. Commercially Confidential Information

Summary statistics will include mean (arithmetic and geometric), SD, CV (arithmetic and geometric), median, minimum and maximum. An exception to this is Tmax where median, minimum and maximum will be presented. Commercially Confidential Information

6.1.3 Model checking procedures

Not applicable.

6.1.4 Graphical presentation of results

Commercially Confidential Information

Overlaying individual plasma concentration-time profiles will also be generated.

6.1.5 Pharmacokinetic / pharmacodynamic interactions

Commercially Confidential Information

7 Statistical methods for Pharmacodynamic (PD) parameters

7.1 Primary objective

7.1.1 Variables

The primary efficacy variable is response rate where a patient will be considered a responder if the percentage reduction from baseline in serum LDH is at least 60% at any time up to and including week 4 for that patient.

The primary efficacy variable for assessing the effect of LFG316 over the entire treatment period is the actual serum LDH value measured at multiple time points during the study.

7.1.2 Descriptive analyses

Unless stated otherwise, summary statistics for PD variables will include sample size (N), mean (arithmetic and geometric), SD, CV (arithmetic and geometric), median, minimum and maximum.

Commercially Confidential Information

For serum LDH baseline will be the average of all pre-dose measurements.

7.1.3 Statistical model, assumptions and hypotheses

Proof of concept will be based on LDH levels during the first four weeks. A positive sign of efficacy is when:

- The estimated median response rate is at least 50%

Commercially Confidential Information

7.1.4 Graphical presentation of results

Commercially Confidential Information

7.1.5 Handling of missing values/censoring/discontinuations

The study aims to replace patients who discontinue before the end of period 1 for reasons other than safety and the primary responder analysis will be based on period 1 completers only, in a per protocol fashion. However further analyses will be performed to assess the effect of including patients with incomplete data on the conclusions drawn from the primary analysis. Lack of efficacy will not be considered a missing value. Even if treatment is discontinued, LDH values should still be assessed in the eight-week follow-up period.

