6.9 Rescue medication

Use of rescue medication must be recorded on the Concomitant medications/Significant non-drug therapies CRF after start of study drug. Additional doses of LFG316 may be administered in case of hemolytic crisis between infusions (as evidenced e.g. by sudden increase in LDH levels, decrease in Hb and based on Investigator's judgment, and can be discussed with Novartis).

Use of eculizumab or other biologics as a rescue medication would lead to treatment discontinuation, and subjects entering the 8 week safety follow-up. Blood transfusions and other therapeutic measures are permitted, as outlined in [Section 6.1.2](#).

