7.1 Discontinuation of study treatment

Subjects may voluntarily discontinue study treatment for any reason at any time.

The investigator must discontinue study treatment for a given subject if, on balance, he/she believes that continuation would be detrimental to the subject's well-being.

Study treatment must be discontinued under the following circumstances:

- Subject withdraws consent
- Pregnancy
- Emergence of the following adverse events:
 - Evidence for invasive Neisseria infection
 - In case of other severe systemic or life-threatening infections, treatment discontinuation should be decided on a case-by-case basis

- Use of prohibited treatment as per [Section 5.2](#).
- Any other protocol deviation that results in a significant risk to the subject's safety

Subjects who discontinue study treatment or who decide they do not wish to participate in the study further should NOT be considered withdrawn from the study UNLESS they withdraw their consent (see [Section 7.3](#)). Where possible, they should return for the 8 week safety follow-up, which includes monitoring of intravascular hemolysis after drug discontinuation. If they fail to return for these assessments for unknown reasons, every effort (e.g. telephone, e-mail, letter) should be made to contact them as specified in [Section 7.2.1](#).

If treatment with LNP023 has to be discontinued prematurely and immediately (i.e., because of a significant safety risk which warrants immediately stopping LNP023 treatment), it is recommended to promptly re-initiate treatment with Standard of Care (SoC), as judged by the investigator.

Close monitoring of patients for signs and symptoms of hemolysis should be performed upon LNP023 discontinuation. It is recommended to monitor at minimum for: increase in LDH, decrease in hemoglobin level and PNH clone size, increase in serum creatinine, thrombosis, and change in neurological/mental status. If serious hemolysis occurs, the Investigator should consider the following supportive treatments (and recording them in the appropriate CRF pages):

- Blood transfusion (packed RBCs), or
- Exchange transfusion if the PNH RBCs are >50% of the total RBCs by flow cytometry,
- Corticosteroids,
- Anticoagulation,
- Any other supportive treatment or therapy as judged by the investigator.

An End of Study (EoS) visit one week after permanent discontinuation of LNP023 should occur for the assessments as specified in the [Assessment schedule](#).

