11.4.3 Handling of missing values/censoring/discontinuations

The study aims to replace subjects enrolled before protocol amendment 5 who discontinue before the end of period 1 for reasons other than safety and the primary responder analysis will be based on period 1 completers only, in a per protocol fashion.

Further longitudinal model analyses performed to assess the effect of missing data on the conclusions drawn from the primary analysis will include, if available, data from any subjects who discontinued early. Lack of efficacy will not be considered a missing value. Even if treatment is discontinued, LDH values should still be assessed in the eight-week follow-up period.

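### The primary response rate counts period 1 completers only, so read literally it drops treatment failures and early responders who stop, and near 50% this can decide proof of concept

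*SAP*

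**What the plan says.** SAP 7.1.1 sets this condition for response: "percentage reduction from baseline in serum LDH is at least 60% at any time up to and including week 4 for that patient" (protocol 11.4.1 agrees). The visible proof-of-concept rule in SAP 7.1.3 and protocol 11.4.2 is "The estimated median response rate is at least 50" per cent. There is no control arm, and about 10 patients are planned.

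On discontinuation, SAP 7.1.5 states that "the primary responder analysis will be based on period 1 completers only, in a per protocol fashion". It aims to replace patients who stop before the end of period 1 for reasons other than safety. The same paragraph adds "Lack of efficacy will not be considered a missing value", and promises that "further analyses will be performed to assess the effect of including patients with incomplete data on the conclusions drawn from the primary analysis". Protocol 11.4.3 carries the same completers rule and the same lack-of-efficacy sentence, but its replacement rule is narrower: "The study aims to replace subjects enrolled before protocol amendment 5 who discontinue before the end of period 1 for reasons other than safety". The SAP has no such limit by amendment.

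Two further protocol provisions bear on who can stop early. Section 7.1: "Subjects may voluntarily discontinue study treatment for any reason at any time". Section 6.9: "Use of eculizumab or other biologics as a rescue medication would lead to treatment discontinuation".

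**The concern.** The completers rule and the lack-of-efficacy sentence pull in opposite directions. A patient who stops in period 1 because the drug is not working is not a completer under the first, but is an observed outcome under the second. The visible text does not define a completer, does not say which sentence governs, and does not place that patient in the denominator. Two programmers could produce different primary rates from the same data.

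The rule also conflicts with the endpoint. Response can be reached at any time up to week 4, so a patient with a 60% fall on Day 8 who stops on Day 20 has a known outcome, yet is excluded.

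Read literally, three groups leave the rate:

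- (a) patients who stop for lack of efficacy;
- (b) patients who receive eculizumab or another biologic as rescue;
- (c) patients who respond and then stop.

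Any of them may also be replaced if the stop is not for safety. Losing (a) and (b) raises the rate, and losing (c) lowers it. The single visible proof-of-concept criterion would then partly reflect who stopped.

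**Working it through.** **No plan figure to reproduce.** The sample-size text in protocol 11.6, the prior and the text after the 50% criterion are redacted. The inputs available are about 10 patients, the 50% cut-off, the responder definition and the completers rule. No dropout rate is given, so 10% is assumed below.

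**Step 1: would these patients have LDH data?** Protocol Table 8-1 schedules LDH on Days 8, 15, 22 and 29, so a patient who stops after Day 8 normally has at least one post-dose value. Missing data is therefore seldom a reason to exclude. Follow-up LDH adds little within the window: the first follow-up visit is about 4 weeks after the last dose, so after a Day 15 dose it falls at about Day 15 + 28 = Day 43, past week 4.

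**Step 2: counts that change the verdict.** Posterior medians assume a flat Beta(1,1) prior, with Jeffreys in brackets.

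| Situation | All treated | Completers only |
|---|---|---|
| One failure stops and is replaced | 5/11: 0.460 (0.456), missed | 5/10: 0.500 (0.500), met |
| Two failures stop, not replaced | 4/10: 0.412 (0.403), missed | 4/8: 0.500 (0.500), met |
| One early responder stops, not replaced | 5/10: 0.500 (0.500), met | 4/9: 0.452 (0.447), missed |

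One unreplaced failure among exactly 10 cannot change the verdict: no count x satisfies both x/10 < 0.5 and x/9 ≥ 0.5.

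**Step 3: chance of meeting 50%.** Let p be the response rate among all treated patients, dr the share of responders who stop after responding, and dn the share of non-responders who stop. The rate among completers is

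q = p(1 − dr) / [p(1 − dr) + (1 − p)(1 − dn)].

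At p = 0.40:

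- dr = 0, dn = 0.10: q = 0.40 / (0.40 + 0.60 × 0.90) = 0.40/0.94 = 0.426.
- dr = 0.10, dn = 0: q = 0.36 / (0.36 + 0.60) = 0.375.

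With replacement, the chance of passing is P(X ≥ 5) for X ~ Bin(10, q). Without replacement, 10 are treated, and each is a responding completer, a non-responding completer or a stopper (trinomial). The result passes if responders are at least half of completers.

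| True rate p | 30% | 40% | 50% | 60% | 70% | 80% |
|---|---|---|---|---|---|---|
| Nobody stops, 10 treated | 15.0 | 36.7 | 62.3 | 83.4 | 95.3 | 99.4 |
| 10% of non-responders stop, replaced | 19.2 | 43.2 | 68.6 | 87.2 | 96.7 | 99.6 |
| 10% of non-responders stop, not replaced | 17.4 | 39.6 | 64.7 | 84.7 | 95.7 | 99.4 |
| 10% of responders stop, replaced | 11.6 | 30.6 | 55.7 | 78.8 | 93.4 | 99.0 |
| 10% of responders stop, not replaced | 10.8 | 28.3 | 51.9 | 74.8 | 90.7 | 98.1 |

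If 10% of both groups stop and are replaced, q = p and nothing shifts.

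**Step 4: same patients, two denominators.** Treat until there are 10 completers. The all-treated rule passes if all responders, including those who stopped after responding, are at least half of all treated (exact recursion).

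| 10% stop among | True rate | All treated | Completers |
|---|---|---|---|
| Non-responders | 40% | 32.6% | 43.2% |
| Non-responders | 60% | 81.0% | 87.2% |
| Non-responders | 80% | 99.2% | 99.6% |
| Responders | 40% | 32.3% | 30.6% |
| Responders | 60% | 80.7% | 78.8% |

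**The case against.** The lack-of-efficacy sentence sits in the section on discontinuations and is probably meant to keep failures in as outcomes. If so, groups (a) and (b) cause no shift and only early responders remain. This stands as a reading of intent. The text does not say it, and it leaves group (c) untouched.

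The SAP also plans to test the effect of including incomplete patients on the primary conclusions. It gives no rule for classifying such a patient. Protocol 11.4.3 describes these as longitudinal model analyses, and SAP 7.1.6 makes longitudinal modelling conditional on its seeming useful. The 50% criterion stays on completers.

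The triggering events may be uncommon. Period 1 lasts 29 days, lack of efficacy is not a mandatory stopping reason, and transfusion or additional LFG316 does not by itself end treatment. This is fair, and no frequency is given. The shifts also need one-sided dropout. The larger failure shifts need replacement, and since enrolment is closed (protocol 3.1) they apply only if replacement has already happened.

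Parts of the analysis-set text are redacted and may define a completer, and a strong prior could move the points at which the verdict changes. That limits the finding to the visible text.

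Finally, changing a primary denominator late in an open-label study can look data-driven, and one could instead keep completers as primary, clarify the wording and add an all-treated sensitivity rate. That would leave the decision on a denominator that discards known outcomes. Dating the change and reporting both rates answers the worry.

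**Conclusion.** The concern holds on the visible text and should be fixed; confidence is medium. A literal completers denominator conflicts with the plan's own sentence on lack of efficacy and with an endpoint that can be reached before a patient stops. One replaced failure, two unreplaced failures or one unreplaced early responder is enough to change the verdict when the result is at the threshold. Under 10% one-sided stopping and a true rate of 40%, the chance of passing moves from 36.7% to between 28.3% and 43.2%, depending on who stops and whether they are replaced. At 80% it stays between 98.1% and 99.6%. These figures are illustrations: the dropout share is assumed, the posterior medians rest on assumed priors, and any further criterion is redacted.

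**What to change.** Put the same text in SAP 7.1.5 and protocol 11.4.3, along these lines:

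- The primary response rate is based on all patients who received LFG316.
- A patient is a responder if an LDH reduction of at least 60% from baseline is recorded up to and including week 4 and before any rescue biologic, whether or not period 1 is completed.
- Patients who stop for lack of efficacy or rescue without such a reduction are non-responders.
- Replacement patients add to the denominator; they do not substitute for those who stopped.

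Report the completers analysis as supportive. For other stops, such as for safety, with no post-dose LDH, show the rate with these patients counted as non-responders and with them excluded. Reconcile the replacement rule, which the protocol limits to subjects enrolled before amendment 5 and the SAP does not.

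No new data are needed. The cost is a SAP module amendment (SAP 1.2 treats a substantial change to the main endpoint as major) and a protocol amendment (section 13.1). The result may be less favourable if failures were the ones who stopped, and slightly more favourable if responders were (step 4). Because the study is open-label and enrolment is closed, date the change and report both rates.
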